2.3. Summary of Findings from Previous Clinical Studies

2.4. Rationale for the Clinical Study

2.5. Risk-benefit Assessment

Current antipsychotics used in patients with schizophrenia although effective are not perfect as they might be associated with different side effects. The development of new, effective therapy with improved safety profile would be a beneficial treatment options for schizophrenia patients. The PDE10 inhibitors, based on several preclinical models, may represent a new approach for treatment of psychosis. The use of treatment with new mechanism of action may exert some risks, which, based on available information, was recognized and the study was design to minimize it.

In a similar phase 2, randomized, placebo-controlled study, the efficacy and safety of a selective PDE10A inhibitor (TAK-063) in patients with an acute exacerbation of schizophrenia were evaluated [25]. In this study, no clinically relevant or consistent differences were observed between study drug and placebo groups for hematologic, renal, or hepatic lab test results, vital signs, or ECG. Most subjects reported AEs that were mild or moderate in severity, and the AEs reported in this study were generally consistent with the previously conducted phase 1 studies [26, 27]. AEs experienced by ≥5% of subjects in the IMP (TAK-063) group were akathisia (placebo: 4.9%; IMP: 13.3%), somnolence (placebo: 2.5%; IMP: 12.0%), dyspepsia (placebo: 7.4%; IMP: 10.8%), headache (placebo: 11.1%; IMP: 7.2%), nausea (placebo: 6.2%; IMP: 6.0%), dystonia (placebo: 1.2%; IMP: 6.0%), and decreased appetite (placebo: 1.2%; IMP: 6.0%). None of the serious adverse event (SAE) was considered related to study drug. The investigated PDE10A inhibitor did not result in any deaths, and most AEs were mild or moderate in severity and did not result in the specific study discontinuation [26, 27].

Phase I study results in healthy volunteers showed that CPL500036 compound is generally safe and well tolerated. Potential risks associated with use of CPL500036 based on most frequently AE occurrence in phase I study, assessed as related or possible related with IMP:

- Drowsiness/somnolence,
- Feeling calm,
- Headache,
- Sensation of cold,
- Sensation of hot/heat.

The intensity of observed AEs was classified as mild or moderate. All the AEs were transient and their frequency decreased after Day 3 of administration (in multiple dosing). The most

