4. STUDY DESIGN

4.1. Overview

This is a double-blind, randomized, placebo controlled, parallel group, dose ranging study to explore the efficacy, safety, tolerability and PK of 2 different doses of CPL500036 (PDE10A inhibitor) in patients with an acute exacerbation of schizophrenia when administered for 28 days.

The study will be conducted at multiple clinical units. Approximately 165 patients will be randomized at a 1:1:1 ratio to receive 20 mg CPL500036, 40 mg CPL500036 or placebo.

The study will comprise of a Screening Period (that will include a prior Medication Washout Period), a Treatment Period and a Follow-up Period.

For the Screening Period, patients will undergo screening assessments from Day -10 to Day -8 in multiple settings (i.e., emergency departments, outpatient clinics, etc.). Rolling admission will be employed in this study. Patients that fulfil all the inclusion criteria and none of the exclusion criteria will immediately be admitted to the Clinical Unit and enter a Medication Washout Period of up to 7 days (Day -7 to Day -1) before the randomization on Day 0. The duration of the Medication Washout Period may be shorter or omitted for non-medicated patients.

During the Treatment Period, patients will be dosed with 20 mg CPL500036, 40 mg CPL500036 or placebo once daily for 28 consecutive days (Day 1 to Day 28). Patients will remain in-house for the duration of the Treatment Period.

Approximately 30% of the patients (17 patients in each of the 3 treatment groups) will undergo extensive PK sampling during the Treatment Period, and the remaining 70% of the patients will only undergo sparse PK sampling.

On Day 29, the patients may resume anti-psychotics treatment. The Investigator will continue to monitor the patient for safety and clinical stability. Patients will be discharged from the Clinical Unit based on local standards of care if the patient is in a stable condition under the regular medication(s).

After discharge from the Clinical Unit, patients will return to the Clinical Unit for 2 once weekly Follow-up Visits, $7 (\pm 1)$ and $14 (\pm 1)$ days after the last dose of the investigational medicinal product (IMP) (Day 35 and Day 42).

Patients that withdraw or are withdrawn from the study will attend an early termination visit at the Clinical Unit and 2 safety Follow-up Visits 7 (\pm 1) and 14 (\pm 1) days after the last dose of IMP.

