4.5. Study Duration

The duration of participation for each subject will be approximately 8 weeks. The estimated study duration includes:

- 7. Screening Period: Up to 10 days.
- 8. Treatment Period: Days 1 to 28.
- 9. Follow-up Period: 7 to 14 days after the post-last dose of IMP (Day 28) Days 35 to 42.

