8.3. Safety Variables

8.3.1. Adverse Events

Adverse event reporting will begin for each subject from the date the informed consent form (ICF) is signed and will continue until the final Follow-up Visit.

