8.3.1.1. Definitions

8.3.1.1.1. Definition of Adverse Event

Any untoward medical occurrence in a subject administered an IMP and which does not necessarily have a causal relationship with this treatment. An adverse event (AE) can therefore be any unfavourable and unintended sign (including an abnormal laboratory finding), symptom, or disease temporally associated with the use of a medicinal (investigational) product, whether or not related to the medicinal (investigational) product.

Other untoward events occurring in the framework of a clinical study will be recorded as AEs, e.g. those occurring during treatment-free periods (including Screening or post-treatment follow-up periods), in association with study-related procedures and assessments, or under placebo. For study drugs, lack of efficacy may be an expected potential outcome and should not be reported as an AE unless the event is unusual in some way, e.g., greater in severity.

Concomitant illnesses, which existed prior to entry into the clinical study, will not be considered AEs unless they worsen during the Treatment Period. Pre-existing conditions will be recorded as part of the subject's medical history.

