3.6. Timing of analysis

Baseline characteristic and efficacy analyses will be performed after the last subject completes a 28-day treatment period. All data until the Day 28 visit will be verified and locked before the unblinding. A safety analysis will be performed after all the data, including follow-up visits will be completed, verified and whole database will be locked.

4. Statistical analysis specifications

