4.8.1. Adverse event analysis

Any undesirable signs, symptoms or medical conditions occurring or worsening of pre-existing conditions between signing informed consent and the first administration of the study medication are considered as pre-treatment AEs. Undesirable signs, symptoms or medical conditions or worsening of pre-existing conditions occurring after the first administration of study medication are considered as treatment emergent adverse events (TEAEs).

A TEAE will be analyzed as related to study medication (i.e. as adverse drug reaction, ADR) if the relationship to study treatment was documented as 'unlikely', 'possible', 'probable', or 'definite' or if the relationship to study treatment is missing.

An overview table presenting the incidence of the following AE categories will be presented. Percentage of patients in each category will be compared between treatments as a difference in proportions between treatments including a 95% CI based on the Agresti – Caffo method (2000):

- All AEs
- Pre-treatment AEs
- Serious AEs (SAEs) (including pre-treatment SAEs)
- Treatment emergent AEs (TEAEs)
- Treatment emergent SAEs (TESAEs)
- Severe TEAEs
- Related TEAEs
- Related severe TEAEs
- TEAEs leading to reduction of dose
- TEAEs leading to interruption of dose
- TEAEs leading to permanent discontinuation (i.e. withdrawal) of study medication
- Related TEAEs leading to permanent discontinuation of study medication
- AEs leading to death (i.e. outcome of AE is fatal)
- TEAEs leading to death
- Related TEAEs leading to death

All treatment emergent AEs (TEAEs) and all serious TEAEs will be tabulated by MedDRA SOC and PT presenting the number and percentage of patients reporting the AE and the number of AEs reported. Additional tables will distinguish the events by whether the AE was related to study medication and by maximum severity.

All AEs documented in the eCRF will be listed by patient. Data listings will include patient ID, treatment group, verbatim term, preferred term, system organ class, start and stop date and relative day of the AE, severity, medications (yes/no), seriousness, action taken with study medication, relationship to study medication, and outcome will be provided. TEAEs will be flagged as such. In addition, separate listings for all SAE's, deaths and AEs leading to discontinuation (action taken with study treatment = drug withdrawn, or AE is reason for early termination) will be presented.

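### The treatment-emergent AE window runs to the final follow-up visit, past the Day 29 antipsychotic restart, and no AE table separates the two periods

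*SAP*

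**What the plan says.** SAP 4.8.1 splits AEs at the first dose. Earlier events are pre-treatment; those "occurring after the first administration of study medication are considered as treatment emergent adverse events (TEAEs"). It gives no limit relative to the last dose, and neither does Protocol 10.11.1.

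The window is closed in practice by data collection. Under Protocol 8.3.1, AE reporting "will continue until the final Follow-up Visit". Protocol 4.5 gives the "Follow-up Period: 7 to 14 days after the post-last dose of IMP (Day 28"), that is Days 35 to 42. Protocol 4.1 places the last visit 14 (± 1) days after the last dose, for completers and for withdrawn patients. Protocol 4.1 also states: "On Day 29, the patients may resume anti-psychotics treatment". This applies to all three arms. SAP 3.6 includes the follow-up data: "A safety analysis will be performed after all the data, including follow-up visits will be completed".

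Protocol 8.3.1.1.1 takes a different view of the same days. It records as AEs "those occurring during treatment-free periods (including Screening or post-treatment follow-up periods"), so follow-up counts there as treatment-free.

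For the overview categories (all TEAEs, serious, severe, related and so on), SAP 4.8.1 plans a "difference in proportions between treatments including a 95% CI" by the Agresti-Caffo method. The SOC and preferred-term tables give counts and percentages only. A TEAE is analysed as related if causality is rated unlikely or higher, or is missing.

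**The concern.** Study drug is given as monotherapy (Protocol 2.5). After Day 28 all arms may take another active drug class, so the last two weeks are more than an ordinary washout. Protocol 2.1 says that existing antipsychotics can cause severe motor side effects. Protocol 2.5 reports akathisia and dystonia in excess of placebo for another PDE10A inhibitor. The events most likely to come from restarted medication are therefore among those of interest for CPL500036.

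Under the SAP rule, an event that starts on Day 36 on a restarted antipsychotic is tabulated as treatment-emergent for the randomized arm. If the investigator rates it unlikely to be related, or leaves causality blank, it also enters the related-TEAE rows. What is at stake is how cleanly the drug-placebo safety comparison can be read. The primary endpoint is not affected.

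**Working it through.** The plan gives no post-treatment AE rate and no figure of its own on this point, so there is nothing to reproduce. The check has three steps.

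**1. Share of the window off study drug.**
- Completer: last dose Day 28, last visit Day 42. (42 − 28)/42 = 14/42 = 33%. With the ± 1 day visit allowance: 13/41 = 32% to 15/43 = 35%.
- Patient stopping on Day 7 or Day 14 and followed for 14 days: 14/21 = 67% or 14/28 = 50%. The share therefore depends on dropout, which may differ by arm.

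**2. Equal post-treatment incidence.** Let p1 and p0 be the on-treatment proportions on drug and placebo. Let q be the fraction of each arm with a first event after treatment, independent of on-treatment events. Then

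p′ = p + (1 − p)q, and p1′ − p0′ = (p1 − p0)(1 − q).

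The inputs are the rates for the other PDE10A inhibitor in Protocol 2.5: akathisia 13.3% vs 4.9%, somnolence 12.0% vs 2.5%. The values of q are assumptions.

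| q (assumed) | Akathisia, drug vs placebo | Difference (points) | Somnolence difference (points) |
|---|---|---|---|
| 0 | 13.3% vs 4.9% | 8.4 | 9.5 |
| 5% | 17.6% vs 9.7% | 8.0 | 9.0 |
| 10% | 22.0% vs 14.4% | 7.6 | 8.6 |
| 15% | 26.3% vs 19.2% | 7.1 | 8.1 |

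With 55 randomized per arm and q = 10%, the expected akathisia counts move from 7.3 vs 2.7 (55 × 0.133, 55 × 0.049) to 12.1 vs 7.9 (55 × 0.2197, 55 × 0.1441). Post-treatment cases would then be about 4.8 of 12.1 on drug and 5.2 of 7.9 on placebo.

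**3. Unequal post-treatment incidence.** With q1 on drug and q0 on placebo, the akathisia difference is [p1 + (1 − p1)q1] − [p0 + (1 − p0)q0].
- q0 = 20%, q1 = 10%: 21.97% − 23.92% = about −2.0 points.
- q0 = 10%, q1 = 20%: 30.64% − 14.41% = +16.2 points.

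So the direction is fixed only when q is similar across arms.

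**The case against.** A fair defence of the SAP has five parts.

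- **The window is bounded.** AE collection stops about 14 days after the last dose in every arm. This stands: the SAP states no end, but there is one in practice.
- **The planned statistic moves little.** It is the risk difference, which falls by 0.4 to 1.3 points in the illustration. The relative risk falls more steeply (2.71 to 1.83, 1.52 or 1.37), but the SAP does not plan ratios. This stands. A reader might also infer that a confidence interval for akathisia is shifted. None is planned: Agresti-Caffo intervals are for the overview categories only.
- **Extrapyramidal effects have their own instrument.** ESRS is rated on Days 1, 7, 14, 21 and 28 and at follow-up, and is summarized by scheduled time point (Protocol 8.3.7 and 10.11.6, SAP 4.8.3.5). For completers, the Day 1 to 28 ratings precede the permitted restart. A reader might infer that the open window would hide an akathisia or dystonia signal; the documents do not support that. But ESRS yields scores rather than AE incidence, and it does not cover events such as somnolence.
- **Some rows are hardly touched, and late events can be found.** TEAEs leading to dose change or discontinuation arise essentially during dosing, and the listings show relative day. True, but the summarized TEAE, serious, severe and related percentages still pool both periods.
- **Late events may be genuine drug effects.** Delayed or withdrawal effects should not disappear. This stands. It argues for keeping the whole-period tables and against a day-after-last-dose cut-off as the only window.

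**Conclusion.** The point holds as a cheap improvement to the safety tables. The SAP's rule counts events on restarted antipsychotics as treatment-emergent, and in some cases as related, and no planned AE table separates them. One third of a completer's window is off study drug. That is time off drug, not time on another antipsychotic, because the restart is permitted and not required.

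The likely effect on the risk difference is modest: 8.4 points falling to between 8.0 and 7.1 for akathisia at an assumed q of 5% to 15%. This rests on another compound's rates, on assumed q, on independence of on- and post-treatment events, and on equal q across arms. A reader might infer that the arms are bound to be pushed together. Only equal or similar q gives that; with unequal q the difference could reverse or grow, as step 3 of the working shows. The supported statement is that the comparison may be distorted, in a direction that pooled tables cannot reveal.

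**What to change.** Amend SAP 4.8.1 before unblinding:

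- **Keep** the whole-period TEAE tables as planned.
- **Add on-treatment tables** (the overview with Agresti-Caffo intervals, and SOC/PT). They cover onset from first dose to the earlier of (a) a pre-specified short interval after the last dose, which the sponsor justifies from its PK data, and (b) the start of another antipsychotic.
- **Add post-treatment tables** for later onset, up to the final follow-up visit.
- **State how partial dates are assigned to a period.** SAP 4.1.5 moves incomplete AE and medication start dates early. The first would pull events into the on-treatment window; the second would close that window sooner.

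No new data are needed. AE onset dates (Protocol 8.3.1.2), dosing dates and times (Protocol 6.7) and concomitant medication (Protocol 5.4.3) are already recorded. The cost is SAP wording and one extra set of tables. The downside is that delayed or withdrawal effects appear in the post-treatment tables and not in the on-treatment ones, so both must be read alongside the whole-period tables. A window chosen after unblinding would be open to challenge.

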8.3.1.3.2. Causality

The Investigator will assess the causality/relationship between the study drug and the AE. One of the categories described in Table 7 should be selected based on medical judgment, considering the definitions below and all contributing factors.

Table 7 Assessment of Relationship of Adverse Events to Investigational Product

Related	A clinical event, including laboratory test abnormality, occurs in a plausible time relationship to treatment administration, and which concurrent disease or other drugs or chemicals cannot explain. The response to withdrawal of the treatment (dechallenge*) should be clinically plausible. The event must be definitive pharmacologically or phenomenologically, using a satisfactory rechallenge† procedure if necessary.	
Probably related	A clinical event, including laboratory test abnormality, with a reasonable time sequence to administration of the treatment, unlikely to be attributed to concurrent disease or other drugs or chemicals, and which follows a clinically reasonable response on withdrawal (dechallenge). Rechallenge information is not required to fulfil this definition.	
Possibly related	A clinical event, including laboratory test abnormality, with a reasonable time sequence to administration of the treatment, but which could also be explained by concurrent disease or other drugs or chemicals. Information on treatment withdrawal may be lacking or unclear.	
Unlikely to be related	A clinical event, including laboratory test abnormality, with a temporal relationship to treatment administration which makes a causal relationship improbable, and in which other drugs, chemicals or underlying disease provide plausible explanations.	
Unrelated	A clinical event, including laboratory test abnormality, with little or no temporal relationship with treatment administration. May have negative dechallenge and rechallenge information. Typically explained by extraneous factors (e.g., concomitant disease, environmental factors or other drugs or chemicals).	

^{*}Dechallenge is when a drug suspected of causing an AE is discontinued. If the symptoms of the AE disappear partially or completely, within a reasonable time from drug discontinuation, this is termed a positive dechallenge. If the symptoms continue despite withdrawal of the drug, this is termed a negative dechallenge. Note that there are

[figure not shown]

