10.11. Safety Analyses

10.11.1. Adverse Events

All AEs will be listed. The number and percent of subjects experiencing an event will be tabulated for each SOC and preferred term. The AEs will also be tabulated according to intensity and causality. An overview table presenting the incidence of AE will be presented. All tables will be prepared separately by number of patients and number of events.

Serious AEs will be listed separately.

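### SAP 4.8.1 counts TEAEs rated 'unlikely' as related adverse drug reactions, and its causality terms do not match Protocol Table 7

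*SAP*

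**What the plan says.** Protocol 8.3.1.3.2 has the investigator rate each event on a five-level scale: "One of the categories described in Table 7 should be selected based on medical judgment". The levels are Related, Probably related, Possibly related, Unlikely to be related and Unrelated. Table 7 describes the top level in these terms: "The event must be definitive pharmacologically or phenomenologically". It describes 'Unlikely to be related' as an event "with a temporal relationship to treatment administration which makes a causal relationship improbable", with other drugs, chemicals or disease as plausible explanations.

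Protocol 10.11.1 then says: "The AEs will also be tabulated according to intensity and causality". It sets no cut between related and not related.

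SAP 4.8.1 does set a cut, and gives the resulting class the name of adverse drug reaction. Membership depends on the recorded rating. An event qualifies "if the relationship to study treatment was documented as 'unlikely', 'possible', 'probable', or 'definite". An event with no recorded rating is placed in the same class. The rule feeds the 'related' rows of the adverse event overview and the SOC/PT tables that split events by whether they were related. The patient listings carry the recorded relationship. SAP 3.4 declares no changes from the protocol.

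**The concern.** An event that the investigator judged improbably caused by the drug is analysed, and named, as an adverse drug reaction. The SAP gives no reason for placing the cut below 'unlikely'. A reader of a related-TEAE table would normally take it to hold events for which the investigator saw a reasonable possibility of a causal link. Protocol 2.5 speaks that way about Phase I, where the listed risks come from events rated related or possibly related. Related rates from this trial would not be on that footing.

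The terms also come from different scales. No mapping from the SAP's four words to the protocol's five labels is given, so the programmer has to supply one.

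At stake are the related-event rates in the safety summary of a placebo-controlled proof-of-concept trial: their level in every arm, the precision of the comparison with placebo, and whether a reader can recover the investigators' grading from the tables.

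**Working it through.** **Step 1: compare the scales.** The plan states no figure to reproduce, so the check starts from the definitions.

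| Protocol Table 7 | Nearest SAP term | Related under SAP 4.8.1? |
|---|---|---|
| Related | 'definite' (by meaning; no shared label) | Yes, if so mapped |
| Probably related | 'probable' | Yes |
| Possibly related | 'possible' | Yes |
| Unlikely to be related | 'unlikely' | Yes |
| Unrelated | none | No |
| (rating missing) | missing | Yes |

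No SAP term is identical to a Table 7 label. Three agree by word root. 'Related' and 'definite' agree only in sense. On that reading four of the five categories, plus missing, are related.

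**Step 2: count the outputs affected.** The SAP 4.8.1 overview has 15 rows. Four use the rule: related TEAEs, related severe TEAEs, related TEAEs leading to permanent discontinuation, and related TEAEs leading to death. The other 11 do not. The related/not-related SOC/PT tables also use it.

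**Step 3: illustrate the size.** The documents give no event rates by causality, so all counts here are assumed. Take n = 55 per arm (Protocol 10.16), with 17 active and 8 placebo patients having an event rated possibly related or higher. Add u patients per arm whose strongest rating is 'unlikely'. The SAP's own interval for a difference in proportions is Agresti-Caffo:

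- p̃ = (x + 1)/(n + 2) in each arm
- CI = p̃₁ − p̃₂ ± 1.96 × √[p̃₁(1 − p̃₁)/(n₁ + 2) + p̃₂(1 − p̃₂)/(n₂ + 2)]

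For u = 0: p̃₁ = 18/57 = 0.3158, p̃₂ = 9/57 = 0.1579, and the standard error is 0.0783. The interval is 0.1579 ± 0.1534, or 0.5 to 31.1 points.

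| u per arm | Active | Placebo | Difference (points) | 95% CI (points) | Ratio |
|---|---|---|---|---|---|
| 0 | 17/55 = 30.9% | 8/55 = 14.5% | 16.4 | 0.5 to 31.1 | 2.12 |
| 6 | 23/55 = 41.8% | 14/55 = 25.5% | 16.4 | -1.4 to 33.0 | 1.64 |
| 11 | 28/55 = 50.9% | 19/55 = 34.5% | 16.4 | -2.2 to 33.7 | 1.47 |
| 17 | 34/55 = 61.8% | 25/55 = 45.5% | 16.4 | -2.3 to 33.9 | 1.36 |

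The observed difference is (17 − 8)/55 = 16.4 points throughout, because equal additions cancel. The rates rise in both arms and the interval widens from about 31 points to about 34 to 36. If the additions are unequal, the difference moves by 1/55 = 1.8 points for each extra patient in one arm, in either direction.

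**The case against.** The strongest defence is that the rule is pre-specified, openly stated and consistently inclusive. Missing ratings count as related, only 'Unrelated' is left out, and the protocol sets no competing cut. Where to draw the line is partly convention, and a wide net can be defended in safety reporting. That stands, and it means the SAP breaks no protocol rule by pooling. It does not justify calling a causally improbable event an adverse drug reaction, nor does it replace the tabulation by causality that Protocol 10.11.1 describes.

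Three stronger readings are tempting, and the documents do not support them.

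- *The SAP drops the protocol's top category.* Table 7 describes 'Related' using the word definitive, and the SAP lists four terms against four categories above 'Unrelated'. 'Definite' is most plausibly the SAP's name for 'Related'. A strictly literal reading would match none of the five labels, 'Unlikely to be related' included, so it cannot be applied to the top category alone.
- *The tables misstate what investigators recorded.* The recorded rating stays in the listings, and 11 of 15 overview rows do not use the rule. The tables pool ratings; they do not alter them.
- *The drug-placebo contrast is diluted.* The SAP compares arms by a difference in proportions, and equal additions leave that unchanged. Only the ratio, which the SAP does not plan, and the precision get worse.

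The eCRF wording is not in the documents. If the eCRF uses the SAP's terms, it is the eCRF and Table 7 that need reconciling. The mismatch then sits elsewhere, but the point about 'unlikely' remains.

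**Conclusion.** The point holds in two parts. First, SAP 4.8.1 labels as adverse drug reactions events that Protocol Table 7 places in its causally improbable category, and it does so by a stated rule. Four of 15 overview rows and the related/not-related tables include such events, and no planned table shows them apart. Second, the SAP's causality terms and the protocol's labels differ and need an explicit mapping.

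The rule raises the reported related rate in any arm that has patients whose strongest rating is 'unlikely', placebo included. How far cannot be known from the documents. Under the assumed counts, 6 to 17 such patients per arm add 11 to 31 points to each arm's rate (6/55 = 10.9%, 17/55 = 30.9%) and take the lower 95% limit from just above zero to just below it, with the difference itself unchanged. That crossing depends on the chosen counts. The general result is a modest loss of precision when additions are equal, and a shift in either direction when they are not.

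This is worth correcting. It does not affect the efficacy analysis or the all-causality safety tables.

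**What to change.** In SAP 4.8.1:

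1. Replace the four terms with the five Table 7 labels and state that 'definite' means 'Related'. If the eCRF uses other labels, give the mapping.
2. Define a related TEAE as Related, Probably related, Possibly related or missing. Define not related as Unlikely to be related or Unrelated. If the sponsor wants the wider definition, add it as an extra overview row labelled as including 'Unlikely to be related'.
3. Add a table of TEAEs by each causality category and treatment arm, with missing shown separately and each patient counted once at the strongest rating. This also delivers the tabulation that Protocol 10.11.1 describes.

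The cost is one sentence and one extra table, with no new data. SAP 3.6 places unblinding after the Day 28 lock and the safety analysis after the full database lock, so the change is best dated before that unblinding.
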